5.2. Rationale

The potential benefits of CAB as a new, LA PrEP regimen with superior efficacy as compared to an active comparator taken daily outweigh the potentially low risks of acquiring HIV and subsequent resistance development. There is a risk for HIV acquisition if the individual does not adhere to the CAB PrEP dosing schedule, and protective levels of CAB decrease to a level where HIV acquisition can occur. There may also be risk for HIV acquisition if the individual does not use other HIV-1 prevention strategies, including knowledge of HIV-1 status, regular testing for other sexually transmitted infections, condom use, etc. A warning and precaution are included in product labelling with recommendation that individuals should be counselled periodically to strictly adhere to the recommended CAB dosing schedule and the use of other prevention strategies. There is also a risk for the development of resistance in individuals with unrecognized or acute HIV-1 infection at the time of starting CAB PrEP.

In addition, there is risk of HIV-1 infection during or following CAB PrEP discontinuation, i.e. during the CAB exposure that is detectable >52 weeks post injection (PK tail), and subsequent emergence of CAB resistant HIV-1 strains. A warning and precaution are included in product labelling with recommendation for monitoring to clinically reassess individuals for risk of HIV acquisition and to test to confirm HIV negative status. Although not treatment limiting, CAB LA usage has the risk of hepatotoxicity and potential for HSRs. This 5-year long prospective, non-interventional study will aim to further understand and quantify the risks in real world clinical settings. The additional data generated will continue to inform clinical practice of CAB LA for PrEP usage.

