 - ii. Describe reasons for discontinuation of CAB LA PrEP
 - iii. Describe characteristics of the individuals who discontinue CAB LA PrEP
- 3) Effectiveness: Monitor for incidence of HIV diagnoses while on CAB for PrEP and describe the timing of incident HIV diagnoses with respect to timing of CAB for PrEP usage
 - a. Describe the proportion and number of incident HIV-1 infections while on CAB for PrEP among individuals in the following groups:
 - i. Infected during OLI
 - ii. Infected while on CAB LA: Incident HIV diagnoses, defined as HIV diagnosed after start of CAB injections while adhering to CAB LA PrEP regimen
 - b. Describe the timing of diagnosis of HIV with respect to timing of CAB for PrEP usage among individuals in the following groups:

- i. Infected during OLI
- ii. Infected while on CAB LA: Incident HIV diagnoses while adhering to CAB LA PrEP regimen
- c. Describe the proportion of incident infections among those who start with OLI and those who go to DTI separately and the timing of diagnosis of incident HIV for the overall group, and separately for the OLI and DTI groups.

The proposed study is a non-interventional study and will collect data from routine clinical practice and plans to capture all prevalent HIV-1 infections, including those captured during baseline. However, there are no plans to collect and store serum samples for subsequent testing as this is not part of standard of care.

- 4) Safety: Monitor for occurrence of DILI and HSRs following CAB LA injections
 - a. Describe the frequency of DILI after starting CAB LA at 6, 12, 24, 36, and >36 months after initiation as defined in Section 7.3.2.
 - i. Incidence proportion and rate of DILI following administration of CAB LA PrEP
 - ii. Incidence proportion and rate of CAB LA discontinuation due to DILI
 - b. Describe the frequency of HSR after starting CAB LA at 6, 12, 24, 36, and >36 months after initiation
 - i. Incidence proportion and rate of HSR following administration of CAB LA PrEP
 - ii. Incidence proportion and rate of CAB LA discontinuation due to HSR
- 5) Resistance: Evaluate incidence of and risk for developing resistance to integrase inhibitors (INSTI) among individuals in the following groups:
 - a. Incident HIV diagnoses while adhering to CAB LA for PrEP and development of resistance during treatment for HIV
 - b. CAB LA PrEP discontinued:
 - i. without subsequent oral PrEP & potential risk for HIV acquisition and viral resistance during CAB LA PK tail

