7.3.2. Outcome definitions

1) Incident HIV diagnoses – confirmation of HIV positive status:

- Frequency (number and proportion) of incident infections during CAB OLI and while adhering to CAB LA PrEP regimen will be assessed. Additionally, frequency of incident infections will be assessed among those initiating CAB OLI and those initiating DTI.
- HIV diagnosis through at least one of the following:
 - Positive HIV-1 antigen/antibody lab results as well as an HIV-RNA-based test; if a combined testing strategy including both tests is not available, testing should follow local guidelines while taking Apretude.
 - One detectable viral load

Incident HIV is any new HIV diagnosis that occurs after the initiation of CAB PrEP, having confirmed HIV negative status using HIV RNA test, at the time of PrEP initiation.

Prevalent HIV is defined as any undiagnosed HIV at the time of PrEP initiation and will be defined as positive HIV antigen/antibody test and/or positive viral load from sample collected at the time of initiation, following first prescription of CAB OLI and separately, following first CAB LA PrEP injection. Note the test result may be reported within 4-6 weeks after the sample was collected. Proportion and number of persons with prevalent and incident HIV will be reported for CAB OLI and CAB LA PrEP separately.

This study is designed to capture data documented in health records in real world clinical settings, provision of 4-6 weeks after starting PrEP for diagnosis included above accounts for time needed to obtain the diagnostic testing results, confirmation and uploading it to the health record. Assessment of 'prevalent infection' vs. 'incident infection' will take into consideration the date the diagnostic test sample was collected and sent to the lab for testing.

2) Proportion of individuals receiving CAB LA PrEP with HIV diagnosis

3) Time to incident HIV diagnosis

- a) Time to diagnosis will be defined as months from first CAB LA injection or OLI till the first confirmed positive HIV-1 antigen/antibody result, detectable viral load and HIV diagnosis.
- b) Time to HIV diagnosis will be shown separately for individuals infected during OLI and while adhering to CAB LA injection schedule.
- 4) ART regimen and VL testing among CAB PrEP users with prevalent and incident infections:

ART regimen and VL testing during the follow-up period for the following groups will be described:

- a) Individuals with incident infections

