Frequency of undiagnosed prevalent HIV at CAB PrEP initiation will be assessed as described for objective 1. The primary effectiveness measure for objective 3 is proportion of individuals with incident HIV diagnosis during OLI and separately during CAB LA PrEP and will be calculated at 6, 12, 24, 36 months and over the entire length of follow-up. The proportion of incident infections among those who start with OLI and those who go to DTI will also be reported separately along with the timing of diagnosis of incident HIV acquisition for the overall group, and separately for the OLI and DTI groups.

Adherence patterns and characteristics of individuals with incident HIV diagnosis will be compared with those without incident HIV diagnosis, using t-test for continuous variables (Wilcoxon rank sum test for not normally distributed variables) or chi-square test for categorical variables. Participant characteristics significantly impacting acquisition of HIV based on univariate analysis will be selected for multivariable analysis. Risk for HIV acquisition and characteristics affecting risk for HIV acquisition will be assessed using negative binomial model with log-link function with binary outcome (HIV diagnosis vs not) if feasible.

Time to HIV diagnosis will be defined as time from first CAB LA PrEP injection to the first HIV diagnosis using laboratory antigen/antibody test, confirmed by viral RNA test. Time to HIV diagnosis will be assessed using Kaplan-Meier curve. Differences in time to diagnosis will be assessed by sex, gender, ethnicity (where available), geographic region, and risk factors (e.g. STI, previous PrEP usage) related, adherence to current PrEP to HIV acquisition. Additionally, time to diagnosis will be shown for people who acquired the infection while prescribed oral CAB lead in (if applicable). Time to diagnosis in this group will be defined as time from first CAB oral prescription to the first positive HIV-1 antigen/antibody lab result, confirmed by viral RNA test.

If feasible, Cox proportional hazards models will be constructed to compare time to HIV diagnosis by subgroup adjusting for additional variables (e.g., sex, ethnicity, (where available) geographic region).

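### Objective 3(b) asks for the timing of HIV diagnosis relative to CAB use, but every defined clock starts at initiation, so it is only partly answered: no defined time places a case within or beyond its dosing interval

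*Protocol*

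**What the plan says.** Section 6, Objective 3 sets out to "describe the timing of incident HIV diagnoses with respect to timing of CAB for PrEP usage". Item (b) repeats this ("Describe the timing of diagnosis of HIV with respect to timing of CAB for PrEP usage among individuals in the following groups") and lists two groups: people infected during oral lead-in (OLI), and "Infected while on CAB LA: Incident HIV diagnoses while adhering to CAB LA PrEP regimen". Neither text says whether timing is counted from the first or the last dose.

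The definitions that follow do choose:
- Section 7.3.2 item 3a: "Time to diagnosis will be defined as months from first CAB LA injection or OLI till the first confirmed positive HIV-1 antigen/antibody result".
- Section 7.6.1, Objective 3, main definition: "Time to HIV diagnosis will be defined as time from first CAB LA PrEP injection to the first HIV diagnosis".
- Section 7.6.1, Objective 3, infections during OLI: "Time to diagnosis in this group will be defined as time from first CAB oral prescription to the first positive HIV-1 antigen/antibody lab result".

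Section 5.2 gives the reason for interest in timing. Acquisition becomes possible if dosing is not kept up and "protective levels of CAB decrease to a level where HIV acquisition can occur". The same section describes a pharmacokinetic tail detectable for more than 52 weeks after an injection.

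Section 7.3.2 item 5 counts an injection 7 or more days late as non-adherence. It defines discontinuation as two injection cycles, about 127 consecutive days, without injection and without oral bridging. Section 7.5 says that injection dates and laboratory data are collected.

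**The concern.** For an injectable given every two months, use is a series of dated injections. Time since the first one measures how long a person has been in the programme. It does not show whether the person was covered when infection was found. A diagnosis soon after an on-time injection and a diagnosis after a missed one mean different things for the product, and the only defined time variable gives them the same value.

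Section 7.6.1 opens by saying that it shows the specific method for each objective. The initiation clock is therefore a rule that the protocol fixes, and an analysis plan that follows it would inherit that clock.

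**Working it through.** **1. Clocks defined.** The three explicit definitions start at first injection or OLI start, at first injection, and at first oral prescription. None starts at the last dose before diagnosis. Section 7.6.1 also promises the timing of diagnosis overall and by OLI or direct-to-injection start, but names no starting point for that output.

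**2. What the first-dose clock hides.** Section 5.1 gives two injections one month apart and then one every two months, so on-schedule injections fall at months 0, 1, 3, 5, ..., 11, 13, 15. Take two diagnoses at month 14:
- Case A, on schedule: last injection at month 13. Gap 14 − 13 = 1 month, about 30 days.
- Case B, month-13 injection missed: last injection at month 11. Gap 14 − 11 = 3 months, about 90 days.

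Both have a time to diagnosis of 14 months.

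**3. Whether the planned groups separate them.** Two months is 2 × 365.25/12 = 60.9 days. A maintenance user who is never 7 or more days late is at most 60.9 + 6 = 66.9, about 67 days from the last injection. If the 127 days are counted from the last injection (an assumption, as the protocol does not give the starting date), an unbridged person becomes a discontinuer at about day 127. Between about day 67 and day 127 a case is neither adhering nor discontinued. Case B, at about 90 days, is in that gap. It is outside the two groups of Objective 3(b) and also outside the discontinued groups of Objective 5(b). If the count starts at the missed due date instead, the gap is longer, not shorter.

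**4. Whether such cases enter Objective 3 at all.** Section 7.3.2 defines incident HIV as any new diagnosis after initiation in a person confirmed negative at the start, and the Kaplan-Meier time in Section 7.6.1 is not restricted to adherent users. Case B is therefore in that analysis. No section says how adhering is judged for a case at the time of diagnosis.

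**5. How many cases.** Section 5.1 cites 0.20 per 100 person-years (cisgender women) and 0.40 per 100 person-years (men who have sex with men and transgender women) in the CAB arms of the pivotal trials.
- 500 × 3 years = 1,500 person-years: 1,500 × 0.0020 = 3 and 1,500 × 0.0040 = 6 cases.
- 500 × 5 years = 2,500 person-years: 2,500 × 0.0020 = 5 and 2,500 × 0.0040 = 10 cases.

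The second line is generous for 500 people, because Section 7.2.1 ends follow-up five years after the first enrolment. Neither line allows for loss to follow-up.

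**6. The plan's own figures.** Table 1 reproduces with exact Clopper-Pearson limits (N = 500 at 1.00%: 0.3255% to 2.3181%). The point does not depend on it, and no sample-size figure changes.

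**The case against.** The strongest reply is that the protocol does address cover. It counts infections during OLI and while adhering separately. It compares adherence patterns between people with and without incident HIV, and examines time to diagnosis by adherence. It assesses resistance in non-adherent people who acquire HIV, and places infections after discontinuation under Objective 5. For an adherent maintenance user the gap since the last injection is at most about 67 days, so little is lost in that group. Objective 3 names no starting point, Section 7.6.1 also plans to look at HIV test timing relative to injection dates, and the dates needed are collected. A per-case listing could be left to an analysis plan that is not shown.

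Much of this stands, and it rules out three stronger readings:
- A reader might infer that time since last injection will never be reported, or that Objective 3 goes unanswered. The documents do not show this. Time from initiation with the OLI/adhering split is a partial answer, and one timing output has no stated starting point.
- A reader might infer that the study cannot tell drug failure from lapsed cover. The adherence analyses bear on that question, and someone unbridged 200 days after the last injection would be classed as discontinued, not pooled with adherent cases.
- A reader might treat 1,500 person-years as a maximum. Both 500 people and 3 years are stated as minimum targets.

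What does not stand is that these elements make the interval unnecessary. Test timing relative to injections answers Objective 1(d), which concerns testing practice among users. An adherence history can class as non-adherent both a person with one late injection a year earlier and a person uncovered at diagnosis. The 67-day bound applies only if adherence is judged at diagnosis, which no section specifies.

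**Conclusion.** The point holds in a limited form. The protocol fixes initiation-based clocks for an objective about timing relative to use, and so answers it only in part. The loss is greatest for cases that are 7 or more days late but short of the discontinuation rule. These belong to neither the adhering nor the discontinued group, and the first-dose clock cannot place them.

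The case count of about 3 to 6 (up to 5 to 10 at five years each) assumes that the pivotal-trial rates carry over to this cohort, and it is illustrative only. At that size the regression models, planned only if feasible, are unlikely to recover the information, and the per-case description carries much of it. The boundaries in days assume a two-month maintenance interval and a 127-day count from the last injection. The point affects no sample-size figure and no clinical rule.

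**What to change.** Keep time from first dose for the Kaplan-Meier analysis. In Section 7.3.2 item 3 and in the Objective 3 analysis of Section 7.6.1:
- For every incident case, add days from the last CAB injection (or last OLI supply) to the last negative sample and to the first positive sample. The two values bracket the time of acquisition, which the diagnosis date alone does not.
- Tabulate cases as within the dosing interval, past due but not discontinued, or after discontinuation. Use the protocol's own 7-day and approximately 127-day definitions, state the date from which the 127 days are counted, and note any oral bridging.
- Name this as the analysis for Objective 3(b), and say that it is descriptive because cases will be few.

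The cost is a few sentences and one listing, from injection dates and laboratory data that are already collected. There is no change to sample size, data collection or participant care.

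### Section 7.3.2 accepts HIV diagnoses that the time-to-diagnosis analysis in Section 7.6.1 does not count as events, and the time origin is unsettled for people who start with OLI, so case counts and times can disagree

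*Protocol*

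**What the plan says.** Section 7.3.2, item 1, sets the case rule as "HIV diagnosis through at least one of the following". The first route is "Positive HIV-1 antigen/antibody lab results as well as an HIV-RNA-based test". It carries a fallback: "if a combined testing strategy including both tests is not available, testing should follow local guidelines while taking Apretude". The second route is "One detectable viral load", with no antigen/antibody result required.

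Section 7.3.2, item 3(a), then defines time to diagnosis as "months from first CAB LA injection or OLI till the first confirmed positive HIV-1 antigen/antibody result, detectable viral load and HIV diagnosis". It does not say whether all three elements are needed or which one supplies the date.

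Section 7.6.1, Analysis for Objective 3, names the proportion with incident HIV as the primary effectiveness measure and gives it no case rule of its own, so the rule in Section 7.3.2 applies. For Kaplan-Meier, the same section defines time to diagnosis as "time from first CAB LA PrEP injection to the first HIV diagnosis using laboratory antigen/antibody test, confirmed by viral RNA test". The Cox models, planned if feasible, use the same time variable. For people infected during OLI, a separate time is defined: "time from first CAB oral prescription to the first positive HIV-1 antigen/antibody lab result, confirmed by viral RNA test". The section also promises timing of diagnosis for the overall group and for OLI and DTI starters separately.

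**The concern.** The primary proportion and the time-to-event analysis are meant to describe the same infections. As written, the proportion uses an either/or rule and the survival endpoint uses a both-required rule. A person can be a case in one and not an event in the other, or be an event in both with different dates. The clock for someone who takes OLI and is diagnosed after injections begin can also start at two places.

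The study expects only a handful of infections. One case that moves between definitions is a sizeable share of the total, and a reader who compares the reported proportion with the curve would have no means of explaining the gap.

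**Working it through.** **The plan's own figures.** Section 7.4.1, Table 1, gives exact Clopper-Pearson limits. With x cases in n people, the lower limit is the 0.025 quantile of Beta(x, n − x + 1) and the upper limit is the 0.975 quantile of Beta(x + 1, n − x). For n = 500 and 1.00%, x = 5, and the limits are 0.3255% and 2.3181%, as printed. All 18 rows of Table 1 reproduce to within 0.0001 percentage points, and so do the 5 rows of Table 2 at the printed precision. The tables are not in dispute.

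**The two case rules applied to the same person.**

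| How the case is recorded | Case under 7.3.2, item 1 | Event in the 7.6.1 main curve |
|---|---|---|
| Antigen/antibody and RNA positive, after first injection | Yes | Yes |
| Viral load detectable, no positive antigen/antibody on record | Yes | No |
| Viral load detectable, antigen/antibody positive later | Yes, from the viral load | Yes, but can be dated at the later result |
| Diagnosed under the local-guideline fallback, no RNA | Yes | No |
| Diagnosed during OLI, before any injection | Yes | No; reported only on the separate OLI clock |

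Rows 2 to 4 come from the conflict in case rules. Row 5 comes from the time origin.

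**Expected number of cases.** Inputs: at least 500 participants (Section 7.4.1); at least 36 months of follow-up (Section 7.6.1); incidence on CAB of 0.40 and 0.20 per 100 person-years in the two pivotal trials (Section 5.1). Assumption: everyone contributes three full years without loss.

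- Person-years: 500 × 3 = 1,500.
- Low: 1,500 × 0.20/100 = 3 cases.
- High: 1,500 × 0.40/100 = 6 cases.

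**Effect of one discordant case.** The protocol gives no number of such cases, so one is an illustration.

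- From 3 to 2 events: 1/3 = 33%. As proportions with exact 95% limits, 3/500 = 0.6% (0.124 to 1.743) becomes 2/500 = 0.4% (0.048 to 1.437).
- From 6 to 5 events: 1/6 = 17%. 6/500 = 1.2% (0.442 to 2.593) becomes 5/500 = 1.0% (0.325 to 2.318).
- With no discordant case the counts agree.

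**Time origin.** For an OLI starter diagnosed after the first injection, Section 7.3.2, item 3(a), allows first injection or OLI, and Section 7.6.1 uses first injection. OLI lasts four weeks (Section 5.1): 28/30.4375 = 0.92 month. That is 0.92/6 = 15% of a 6-month window and 0.92/12 = 8% of a 12-month window. The choice moves event times and the risk set. It changes the event count only for people diagnosed before any injection.

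**The case against.** Several points on the other side are sound. The study tests no hypothesis, the primary effectiveness measure is the proportion, and the Cox models are conditional on feasibility, so the conflict touches a descriptive curve and leaves the primary count as Section 7.3.2 defines it. The separate clock for people infected during OLI is deliberate and appears in both sections, so it is not a contradiction. What it leaves open is the OLI starter diagnosed after injection, and how cases diagnosed during OLI enter the timing for the overall group. Detail can be left to an analysis plan, but here the protocol states two incompatible rules, and an analysis plan could follow one only by departing from the other.

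A reader might infer three stronger things. The first is that the counts will disagree. The documents show only that they can: if every case has antigen/antibody plus RNA confirmation and none falls in OLI, they match. The second is that the outcome definition rests on a single viral load; that is one of two routes. The third is that false-positive RNA results would make up a large part of the cases. The documents do not support this. They give neither an assay specificity nor a number of RNA tests per person, testing follows guidelines and local practice (Section 7.1), and a positive sample taken at initiation is classed as prevalent, not incident.

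Nor do the documents call for a compulsory second positive sample. The study works from routine records with no stored serum, and such a rule could remove true cases from a very small count.

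**Conclusion.** The point holds as an inconsistency between two stated definitions. A case diagnosed by viral load alone, or under the local-guideline fallback without RNA, counts in the primary proportion but can be missed or dated late in Kaplan-Meier and Cox. Item 3(a) of Section 7.3.2 adds a third wording that does not settle the matter. The origin is ambiguous by about four weeks for OLI starters diagnosed after their first injection, and cases diagnosed during OLI have no place in a curve that starts at injection.

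One discordant case would change the event count by 17% to 33%. This rests on 500 people, complete three-year follow-up and pivotal-trial incidence. Section 7.8 expects loss to follow-up; fewer person-years would mean fewer cases and a larger effect per case, while enrolment above 500 would work the other way. How many discordant cases will occur is unknown and may be none. The matter should be corrected, but it does not invalidate the primary measure.

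**What to change.** 1. Use one case definition in Sections 7.3.2 and 7.6.1 for the proportion, Kaplan-Meier and Cox. The either/or rule in Section 7.3.2, item 1, can serve, with item 3(a) and the Objective 3 text referring to it and not restating it.
2. Set the event date as the collection date of the first positive sample. Section 7.3.2 already relies on collection dates to separate prevalent from incident infection, so no new data item is needed.
3. State one time origin per analysis population: first CAB dose, oral or injected, for the overall group; first injection for the on-injection analysis. The existing OLI clock can stay for people infected during OLI.
4. Keep single unconfirmed viral-load cases in the main count, and add one sensitivity row that excludes them.

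The cost is a wording amendment to two sections and one extra table row. No case is dropped from the primary measure, and no extra testing is asked of sites.
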